Administrative updates, editorial changes, and style and formatting revisions have been made to improve clarity and consistency throughout the document. Significant changes are described in the table below. Changes in sections of the protocol body were also made in the protocol synopsis and elsewhere in the document, as applicable. Changes in the schedules of assessments have been updated to be current with the revised study plan and assessment schedule. Please see body of the protocol and the schedules of assessments for additional details. Added text is presented in bold format.

**APPENDIX I: SUMMARY OF CHANGES IN
PROTOCOL 2012-001 AMENDMENT 2**

Study 2012-001 was amended to incorporate FDA requested changes/additions, specifically with regard to the definition of dose-limiting toxicities as applied to the Phase 1b component of the study and the incorporation of specific guidelines for the Prophylaxis and Management of Tumor Lysis Syndrome (TLS). The key changes in Amendment 2 are listed below:

1. Study Synopsis (Study Design) and Section 6.3 Dose-Limiting Toxicity: The text was edited to classify Grade ≥ 4 abnormalities in serum creatinine or electrolytes as DLTs; Grade ≥ 3 acute kidney injury defined as creatinine $> 3 \times$ baseline or > 4.0 mg/dL of any duration is to be considered a DLT; and occurrence of Grade ≥ 3 nausea, vomiting, constipation or diarrhea of > 7 days duration in spite of optimal management, including a 5-HT₃ antagonist and aprepitant for nausea and vomiting, and loperamide (e.g., Imodium®) and diphenoxylate/atropine (e.g. Lomotil®) for diarrhea is to be considered a DLT.
2. Sections 6.5 and 6.6.1: Text was added to provide guidance for monitoring/prophylaxis and treatment of tumor lysis syndrome.

Administrative updates, editorial changes, and style and formatting revisions have been made to improve clarity and consistency throughout the document. Significant changes are described in the table below. Changes in sections of the protocol body were also made in the protocol synopsis and elsewhere in the document, as applicable. Added text is presented in bold format.

**APPENDIX I: SUMMARY OF CHANGES IN
PROTOCOL 2012-001 AMENDMENT 1**

Study 2012-001 was amended to implement a new starting dose for Oprozomib Tablets for both dosing schedules based on dose-escalation data from ongoing Study 2011-001. This and other key changes in Amendment 1 are listed below:

1. Global change: Starting dose of 150 mg was changed to 210 mg for both oprozomib dosing schedules. This update was made based on dose-escalation data from ongoing Study 2011-001 from both tablet and product-in-capsule (PIC) formulations.
2. Global change: Changed units for absolute neutrophil count (ANC) and platelet counts from [value] $\times 10^9/L$ to standard units, [value] cells/mL.
3. Study Synopsis (Test Product, Dose, and Mode of Administration): Removed specific dexamethasone oral tablet strengths (4 mg and 6 mg). This text did not appear in the protocol body.
4. Section 1.4.1: Added dose rationale for 210 mg starting dose of Oprozomib Tablets based on preliminary safety results from Study 2011-001, PK data demonstrating comparable exposures between the tablet and capsule, and rationale for the combination of oprozomib with low-dose dexamethasone as a means to reduce gastrointestinal (GI) toxicity.
5. Section 3.4, Appendix A and Appendix B (footnote 1): Added that subjects continuing on study treatment and whose disease has not progressed 1 year after starting study treatment will reduce the frequency of their visits (on Day 1 of their next scheduled cycle) to every 4 weeks instead of every 2 weeks, with adequate drug supply for 2 cycles of treatment. Also clarified that disease response will be assessed every 8 weeks (4 cycles) after 1 year on therapy.
6. Section 4.1: Clarified in Inclusion Criterion #5 that bilirubin must be ≤ 1.5 times the upper limit of normal (ULN) *in the absence of Gilbert's disease or hemolysis*.
7. Section 4.2: Clarified in Exclusion Criterion #3 that glucocorticoid therapy within 14 days prior to randomization that exceeds a cumulative dose of 160 mg of dexamethasone or equivalent is not allowed.
8. Section 4.2: Added Exclusion Criterion #10, uncontrolled hypertension or uncontrolled diabetes.
9. Section 4.2: Deleted Exclusion Criteria #14, patients with pleural effusions requiring routine thoracentesis, and #15, patients with ascites requiring routine paracentesis.
10. Section 4.2: Updated Exclusion Criterion #18 to add "increased patient risk" to the criterion.

11. Section 6.1: Appendices A and B (footnote 23): Provided clarification that dexamethasone must be taken *at least 30 minutes* prior to oprozomib.
12. Section 6.1: Specified that oprozomib will be administered in combination with dexamethasone at 20 mg orally (*or intravenously, if tablets are unavailable or subject cannot tolerate tablets*).
13. Section 6.2.2: Added that intrasubject dose escalation to the recommended Phase 2 dose may be permitted once that dose has been determined and after discussion between the treating physician and Onyx medical monitor.
14. Section 6.3: Added note that \geq Grade 3 dexamethasone-related hyperglycemia is not considered a DLT.
15. Section 6.3: Added note that Grade 3 fatigue lasting $<$ 14 days is not considered a DLT.
16. Section 6.6.1: Added recommended concomitant medications, valacyclovir and lansoprazole, for prevention of herpes zoster and peptic disease, respectively.
17. Sections 7.3.1–7.3.4, Appendix A and Appendix B (footnotes 15-18), and Appendix G: Updated protocol body and schedule of assessments to provide clarification and flexibility around PK and PDn sampling timepoints. For Phase 2 subjects, also provided clarity that subjects must fast before and after study drug administration on PK sampling days.
18. Section 9.3.1: Revised the text for how AEs are captured for subjects who do not receive any study drug.
19. Appendix A: Removed redundant term, cytogenetics, to clarify that FISH is the cytogenetic technique that will be used..
20. Appendix A: Added missing Cycle 2, Day 3 and 4 column that includes administration of oprozomib, administration of optional antiemetics, and recording of AEs and concomitant medications.
21. Appendices A and B (footnote 9): Added that serum chemistry and complete blood count (CBC) on Cycle 2, Day 5 will be completed for Phase 2 only (if PK or PDn sample is being collected).
22. Appendices A and B (footnote 12): Added that, if present at Baseline, bone lesions must be monitored every 2 cycles throughout the study.
23. Appendices A and B (footnote 13): Provided clarification that, in addition to Screening and End of Study assessments, subjects with plasmacytoma(s) at Baseline must also be monitored *every 2 cycles* throughout the study per IMWG response criteria.
24. Appendices A and B (footnote 14): Add clarification that bone marrow aspirate will also be collected at the time of progression (may be at time of treatment discontinuation or during long-term follow up) for subjects who have signed the separate consent.
25. Appendix B: Added missing timepoint for Cycle 2, Day 1 PDn/Proteomic analyses.

26. Appendix F (EBMT criteria): Updated criteria for minimal response based on Kyle 2009 article on response assessment in multiple myeloma.

Minor editorial changes and updates to style and formatting have been made to improve clarity and consistency throughout the document.

Detailed changes are described in the table below. Changes in sections of the protocol body were also made in the protocol synopsis and elsewhere in the document, as applicable.

Deleted text is presented in strikethrough format. Revised text is presented in bold format.

1 INTRODUCTION

This statistical analysis plan (SAP) was prepared for an abbreviated clinical study report (aCSR) in accordance with Protocol ONX-2012-001, dated 26 June 2014 (amendment 3), and describes the analyses of data collected within the scope of the study. Any changes that are made to the planned analyses after the SAP is finalized, along with an explanation as to when and why they occurred, will be noted in the abbreviated clinical study report produced for the study. Any changes made to the planned analyses that are in the protocol will be identified and documented in this document.

2 STUDY OVERVIEW

2.1 Overall Study Design

This study is an open-label, Phase 1b/2, multicenter study in which subjects will receive oprozomib (OPZ) administered orally once daily in combination with dexamethasone (DEX) on 2 different treatment schedules. Subjects will receive OPZ on Days 1–5 of a 14-day cycle in combination with 20 mg DEX on Days 1, 2, 8, and 9; or OPZ on Days 1, 2, 8, and 9 of a 14-day cycle in combination with 20 mg dexamethasone on Days 1, 2, 8, and 9. Both the Phase 1b and Phase 2 portions of this trial will be open to subjects with relapsed and/or refractory multiple myeloma.

Treatment will be administered in 14-day cycles until disease progression, unacceptable toxicity, or study treatment discontinuation for any reason.

Disease response assessments will be performed every 4 weeks for the first year through Cycle 26 and then every 8 weeks thereafter according to the IMWG-URC. In addition, nCR and MR will be assessed per the modified EBMT criteria.

A minimum of 3 subjects will be entered within each dose cohort, to be expanded up to 6 subjects if DLTs are observed. Assessment of DLTs will occur during the first 14 days of treatment (or Cycle 1) or the first 14 days of treatment with the step-up dose to be

studies (Cycle 2). Any subject who develops a DLT after receiving at least 1 dose of OPZ will be considered evaluable. Any subject who does not develop a DLT, but has not received all planned doses of OPZ and DEX will be considered unevaluable for the dose escalation decision and will be replaced.

If none of the first 3 subjects in a cohort experiences a DLT in the first cycle, enrollment will commence at the next planned dose level. If 1 of 3 subjects enrolled in a cohort experiences a DLT during the first treatment cycle, the same cohort will be expanded up to 6 evaluable subjects. If 1 of 6 subjects experiences a DLT during the first treatment cycle, the next cohort will enroll at the next higher dose level. If 2 or more subjects in a cohort experience a DLT in the first treatment cycle, the MTD will have been exceeded, additional enrollment within the cohort will cease, and dose escalation will stop.

If 2 or more subjects experience a DLT at a given dose, additional subjects will be added to the preceding dose group if there are fewer than 6 subjects in that cohort, for a minimum of 6 subjects treated at that dose in order to determine the MTD. The MTD will be defined as the highest dose in which a DLT is observed in less than 2 of 6 subjects. At least 6 subjects must be treated at the MTD for a minimum of 1 cycle to establish this dose as tolerated.

The initial cohort will be entered at a dose level of 210 mg. All subsequent cohorts will be escalated by 30 mg until the MTD is determined. There will not be a predefined maximum dose to be studied.

2.2 Study Objectives

2.2.1 Primary Objectives

Phase 1b:

- To determine the MTD and recommended Phase 2 dose (RP2D) of OPZ given orally, once daily, on 2 different schedules: 5 consecutive days every 14 days (bimonthly; 5/14) or 2 consecutive days every 7 days (weekly; 2/7) for a 14-day treatment cycle, both schedules given in combination with DEX.

- To evaluate safety and tolerability

Phase 2:

- To estimate the overall response rate (ORR), defined as the proportion of subjects with the best overall response of stringent complete response (sCR), complete response (CR), near complete response (nCR), very good partial response (VGPR), and partial response (PR) as defined by the International Myeloma Working Group–Uniform Response Criteria (IMWG–URC) and modified European Group for Blood and Marrow Transplantation (EBMT) criteria.
- To evaluate safety and tolerability

2.2.2 Secondary Objectives

- To evaluate PK of OPZ tablet and OPZ ER tablet
- To estimate clinical benefit rate (CBR), defined as ORR plus minimal response (MR), as defined by the EBMT criteria
- To estimate the duration of response (DOR)
- To estimate progression–free survival (PFS)
- To estimate time to progression (TTP)

2.3 Sample Size Justification

For the Phase 1b portion of the study, it is estimated that up to approximately 60 subjects (approximately 30 subjects per treatment schedule) will be required to determine the recommended Phase 2 dose for each treatment schedule. This is based on an estimate that up to 5 cohorts will be enrolled per treatment schedule, with up to 6 evaluable subjects per cohort.

For the recommended dose group (dose escalation cohort plus Phase 2 cohort), the null (H_0) and the alternative (H_A) hypotheses are as follows:

$$H_0: \text{ORR}_{\text{Cd}} \leq 15\%$$

$$H_A: \text{ORR}_{\text{Cd}} > 15\%$$

With a sample size of 46 subjects (6 evaluable dose escalation subjects + 40 Phase 2 subjects enrolled at the recommended dose), a 1-sample exact binomial test with a 1-sided significance level of 5% will have 77% power at an ORR of 30%. If at least 12 of the 46 subjects have a best overall response of PR or better, then the null hypothesis will be rejected and it will be inferred that the ORR is $> 15\%$.

The total study sample size will depend on the number of dose levels required to establish the recommended dose for each schedule and the number of schedules initiated in the Phase 2 portion of the study. The study will enroll approximately 140 subjects.

3 STUDY ENDPOINTS

3.1 Primary Endpoints

Phase 1b:

- Dose-limiting toxicities identified to determine the MTD and RP2D, defined as the highest dose at which $< 33\%$ of subjects experience DLTs after 1 cycle (14 days) of treatment.
- Safety and tolerability

Phase 2:

- Overall response status, to determine whether a subject has a best response of sCR, CR, nCR, VGPR, or PR, as defined by IMWG-URC and EBMT criteria (nCR)
- Safety and tolerability

3.2 Secondary Endpoints

Phase 1b/2:

- Pharmacokinetics of OPZ tablet and OPZ ER tablet

Phase 2:

- Clinical benefit response status, to determine whether a subject has a best response of sCR, CR, nCR, VGPR, or PR, as defined by IMWG–URC and EBMT criteria (MR and nCR)
- Duration of response
- Progression–free survival
- Time to progression

4 ANALYSIS POPULATIONS

All subjects who receive at least 1 dose of study treatment will be considered evaluable for both the efficacy and safety analyses (Safety Population). The Safety Population will be the primary population for all safety and efficacy data presented (Phase 1 and Phase 2).

5 ANALYTIC DEFINITIONS

5.1 Study Day 1

Study day 1 corresponds to the date of the first dose of study drug.

5.2 Study Day

For events, assessments, and interventions after study day 1, study day represents the elapsed number of days from study day 1, inclusive:

$$\text{Study Day } n = (\text{Date of assessment} - \text{Date of Study Day 1}) + 1 \text{ day}$$

Unless otherwise specified, the timing of all study-related events, assessments, and interventions will be calculated relative to study day 1. Study day –1 will be the day before study day 1, and in general for assessments prior to study day 1, study day is defined as:

$$\text{Study Day } n = (\text{Date of assessment} - \text{Date of Study Day 1})$$

For listings (such as for adverse events) that include the derivation of “days since last dose,” this is defined as event date – date of last dose. Events that occur on the same day

as the last dose of study drug will therefore be described as occurring zero days from the last dose of study drug.

5.3 Baseline

Unless otherwise specified, the baseline value is defined as the last assessment prior to the first dose of OPZ and DEX.

6 INTERIM ANALYSIS AND EARLY STOPPING GUIDELINES

There are no formal interim analyses planned for this study. A Cohort Safety Review Committee (CSRC) will review the clinical and laboratory data of each dose cohort before escalating the OPZ dose to the next dose cohort.

7 STATISTICAL METHODS

7.1 General Considerations

This statistical analysis plan is being generated prior to locking the study database. It specifies the main efficacy and safety analyses to be performed.

All statistical summaries and analyses will be performed in SAS[®] version 9.3 or higher (SAS Institute Inc., Cary, NC, USA) on a PC platform.

In general, summaries of all data will be presented by schedule and dose groups, defined as initial dose level cohort for phase 1 and recommended dose cohort for phase 2. In addition, some summaries will include the combined recommended dose cohort from phase 1 and 2 and total cohorts (all subjects by schedule).

Summary statistics will be provided for selected endpoints. For continuous variables, the number of subjects with non-missing data (n), mean, standard deviation, median, minimum, and maximum will be presented. For discrete data, the frequency and percent distribution will be presented. Unless otherwise indicated, percentages will be calculated

based upon the number of subjects in the Safety Population in each dose group as the denominator.

Confidence intervals, when presented, will be constructed at the 95% level. For binomial variables, exact distribution methods will be employed. The distribution of time-to-event endpoints will be summarized by Kaplan-Meier method. Quartiles including median will be estimated by Kaplan-Meier method along with their 95% confidence intervals.

Individual subject data recorded on the electronic case report forms (eCRFs) and any derived data will be presented by dose cohort and subject in data listings.

7.2 Disposition of Subjects

The following subject disposition information will be summarized for all subjects by each of the schedule and dose group and for the combined dose groups (total group).

- number of treated subjects
- number (%) of subjects who discontinue from the study drug
- primary reason for study drug discontinuation
- number (%) who had an End of Study visit
- reason for no End of Study visit

7.3 Demographic and Baseline Characteristics

7.3.1 Demographic and Baseline Characteristics

The following demographic and baseline characteristics will be summarized for the Safety Population.

- Age (years) and age categorized (years) as <65, 65 - <75, and ≥ 75
- Sex

- Ethnicity
- Race
- Baseline ECOG performance status
- Baseline fertility status
- Baseline weight (kg)
- Baseline height (cm)

7.3.2 Medical History

The number (%) of subjects who experienced a prior disease or disorder will be summarized by body system for the Safety Population.

7.3.3 Disease Characteristics

The following disease characteristics will be summarized for the Safety Population.

- ISS at initial diagnosis and at Screening
- Time (years) since initial diagnosis, defined as date of informed consent signed minus date of diagnosis
- Category of multiple myeloma
- Heavy chain and light chain status
- Plasma cell involvement (%) as assessed with bone marrow assessment (< 50%, ≥ 50%, unknown or missing)
- FISH (standard risk, high risk, unknown or not done)
 - High risk: with one of the following abnormalities: t(4;14), t(14;16), del(17p;13), or 1q21 amplification
 - Standard risk: none of the high risk finding
- Baseline β 2 microglobulin (mg/L) (< 5.5 mg/L versus ≥ 5.5 mg/L)

7.3.4 *Prior Cancer Therapies*

The following prior cancer therapy data will be summarized for the Safety Population:

- Number (%) of subjects with at least one prior:
 - Chemotherapy
 - Transplant
 - Radiotherapy
 - No prior therapy
- Number of regimens of prior treatment (1, 2, etc) for multiple myeloma and number of prior drugs

7.4 *Treatments and Medications*

7.4.1 *Study Drug Administration*

The overall extent of study treatment exposure and dose information will be summarized for the Safety Population for both OPZ and DEX.

- Duration of treatment (weeks), defined as (date of last dose – date of first dose + 1) divided by 7 for OPZ and DEX
- Total number of treatment cycles during which one full daily dose of OPZ and DEX was taken by the subject.
- Number (%) of subjects dosed by cycle, where a subject will be considered to have been dosed in a cycle if the subject receives at least one full daily dose of OPZ and DEX.
- Total doses received across all cycles of OPZ and DEX
- Dose modifications of study drug based on AE action taken data

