6.4.1.1 Dose Modification for Hematologic Toxicities

[Table 7](#) summarizes hematologic toxicities and oprozomib dosing actions that should occur in the event of toxicities.

Table 7: Guidelines for Dose Modification for Hematologic Toxicities

Toxicity	Oprozomib Dosing Action
ANC \geq 500 cells/mcL	Continue at full dose
ANC < 500 cells/mcL for less than 7 days	Hold dose. When ANC \geq 500 cells/mcL, resume at full dose.
ANC < 500 cells/mcL for 7 days or longer	Hold dose. When ANC > 500 cells/mcL, resume at 1 dose decrement.
Grade 3 febrile neutropenia	Hold dose. When ANC \geq 1000 cells/mcL and fever has resolved, resume at 1 dose decrement.
Platelet count < 50,000 cells/mcL and \geq 25,000 cells/mcL without evidence of bleeding	Continue at full dose
Platelet count < 50,000 cells/mcL and \geq 25,000 cells/mcL with evidence of bleeding	Hold dose. When platelet count returns to > 50,000 cells/mcL and bleeding stops, resume at 1 dose decrement.
Platelet count < 25,000 cells/mcL for < 7 days without evidence of bleeding	Hold dose. When platelet count \geq 25,000 cells/mcL, resume at full dose.
Platelet count < 25,000 cells/mcL for \geq 7 days with or without evidence of bleeding	Hold dose. When platelet count \geq 25,000 cells/mcL, resume at 1 dose decrement.

ANC = absolute neutrophil count.

Additional guidance regarding hematologic toxicities and dosing actions is as follows:

- Non-treatment-related events: If the toxicity resolves to \leq Grade 1 or baseline and the toxicity is not treatment related, oprozomib may be restarted at the same dose level.
- If required by continued or recurrent toxicity, a second or third dose reduction may be permitted down to a minimum dose of 150 mg after discussion with the **Sponsor** medical monitor. If the subject has not had 3 reductions but is at a dose level of 150 mg, an additional reduction may occur via reducing dose intensity (see [Section 6.4.1](#)). No more than 3 dose reductions will be permitted in an individual subject on study; if toxicity continues, the subject should be removed from the study.
- If the subject tolerates the reduced dose for 1 cycle, the subject's dose may be escalated to the dose prior to the dose reduction.
- If there is no resolution of toxicity after 2 weeks of withholding treatment (up to 3 weeks if an infection is being treated), the subject will be discontinued from the study.

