9. ADVERSE EVENTS

9.1 ADVERSE EVENTS DEFINITIONS

An AE is any untoward medical occurrence in a study subject administered an investigational product(s), regardless of the causal relationship with treatment.

An AE, therefore, can be any unfavorable and unintended sign (including laboratory finding), symptom, or disease temporally associated with participation in an investigational study, whether or not considered treatment related. In addition to new events, any increase in the severity or frequency of a preexisting condition that occurs after the subject signs a consent form for participation is considered an AE. This includes any side effect, injury, toxicity, or sensitivity reaction. All reported AEs will be coded using Medical Dictionary for Regulatory Activities (MedDRA).

Laboratory findings should not be recorded as AEs unless corrective action is required (e.g., transfusions, initiation of antibiotics or treatment regimens, hydration) or the event is deemed clinically significant by the treating physician.

Any condition, laboratory abnormality, or physical finding with an onset date prior to the subject signing consent for study participation is considered to be preexisting in nature and part of the subject’s medical history.

An unexpected AE is any AE, the specificity or severity of which is not consistent with the current Investigator’s Brochure (IB) or prescribing information for a marketed compound; or that adds significant information on specificity or severity of a known, already-documented AE. For example, an event more specific or more severe than described in the Investigator’s Brochure would be considered “unexpected.”

Whenever possible, the NCI-CTCAE (Version 4.03) should be used to describe the event and for assessing the severity of AEs ([National Cancer Institute 2010](#)). **The National Cancer Institute Common Terminology Criteria for Adverse Events does not use to the term “intermittent” and this term must not be used to describe AEs.** Any AEs representing a change in the NCI-CTCAE grade need to be reported on the AE eCRF. For AEs not adequately addressed in the NCI-CTCAE, the table below ([Table 12](#)) may be used.

Table 12: Adverse Event Severity Grades

Severity	Description
GRADE 1 - Mild	Asymptomatic or mild symptoms; clinical or diagnostic observations only; intervention not indicated
GRADE 2 - Moderate	Minimal, local or noninvasive intervention indicated; limiting age-appropriate instrumental ADL

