10.3.3 SAFETY ANALYSIS

Safety and tolerability assessments will include extent of exposure to study treatment, AEs (including the DLT assessment period DLTs and SAEs), laboratory values, vital sign results, and ECGs. Safety data will be examined on an ongoing basis to ensure subject safety.

Extent of exposure to the study treatment will be summarized using descriptive statistics (n, mean, standard deviation, median, and range). Percent of subjects and number of cycles with dose holds and reductions will be calculated by treatment group.

Adverse events will be coded using MedDRA. Treatment-emergent AEs are defined as AEs occurring from the first dose of study treatment through 30 days after the last dose of study treatment. An AE that is present before the first administration of study treatment and subsequently worsens in severity between the first dose of study treatment and 30 days after the last dose of study treatment is also considered to be treatment emergent. Adverse events will be summarized by MedDRA system organ class and preferred term for the number and percentage of subjects who experienced the event. A subject reporting the same AE more than once will be counted only once when calculating (1) within a given system organ class and (2) within a given system organ class and preferred term combination. For such cases, the

maximum NCI-CTCAE toxicity grade and strongest causal relationship to study treatment for the event will be used in the incidence calculations. Treatment-emergent AEs will be tabulated to examine their frequency, severity, and relationship to study treatment. Additional summaries will be provided for SAEs and events resulting in the permanent discontinuation of treatment. All AEs will also be included in individual subject listings.

A listing of subjects who experience a DLT during the DLT assessment period of the dose- escalation portion will be generated along with the results associated with the PK/PDn parameters considered.

Laboratory parameters will be summarized using descriptive statistics and by postdose shifts relative to baseline. Vital sign results will also be summarized descriptively for each scheduled protocol time point. Changes will be calculated relative to the values collected at baseline, defined as the last assessment taken prior to the first dose of study drug on Day 1 of Cycle 1.

The analysis of the locally performed ECGs will involve descriptive statistics.

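### SAP 7.4.1 limits the protocol's summary of dose holds and reductions to AE-linked actions, plans no count of affected cycles, and does not record the change

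*SAP*

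**What the plan says.** Protocol 10.3.3 (Safety Analysis), under extent of exposure: "Percent of subjects and number of cycles with dose holds and reductions will be calculated by treatment group". It does not restrict these to events recorded as adverse events.

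SAP 7.4.1 (Study Drug Administration) says exposure and dose information "will be summarized for the Safety Population for both OPZ and DEX", then lists five items: duration of treatment, number of cycles, subjects dosed by cycle, total doses and dose modifications. Four of them matter here:

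- Dose modifications: "Dose modifications of study drug based on AE action taken data".
- Number of cycles: "Total number of treatment cycles during which one full daily dose of OPZ and DEX was taken by the subject".
- Dosed in a cycle: a subject counts "if the subject receives at least one full daily dose of OPZ and DEX".
- Total doses: "Total doses received across all cycles of OPZ and DEX".

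SAP Section 1 undertakes to identify and document in the SAP any change to analyses planned in the protocol. None is documented for this summary.

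**The concern.** The protocol's measure concerns what happened to dosing. The SAP's measure concerns what was entered in the action field of an adverse event record. The two agree only if every hold and reduction is tied to a recorded adverse event, and the protocol's own rules do not ensure that. If AE action fields are completed correctly, the error runs one way: holds and reductions are missed, not invented, so the regimen looks better delivered than it was.

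Safety and tolerability are a primary objective in both phases, and Protocol 10.3.3 names extent of exposure as part of that assessment. What is at stake is a descriptive table under a primary objective, and whether a reader of the abbreviated report can find the measure the protocol announced.

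**Working it through.** No sample size, power or event count is involved and there is no plan figure to reproduce. The check sets the passages side by side.

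**1. Does the protocol commitment apply to this SAP?** The SAP cites Amendment 3; the protocol at hand is Amendment 4. The Amendment 4 summary of changes (Appendix N) lists no change to Section 10, so nothing suggests that the commitment in 10.3.3 was added or altered after the SAP's reference version.

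**2. Are holds always tied to an adverse event?** Table 7 in Protocol 6.4.1.1 sets the dosing action from laboratory values. One row is "ANC < 500 cells/mcL for less than 7 days", with a hold and then resumption at full dose. Platelets below 25,000 cells/mcL for less than 7 days without bleeding are treated in the same way. Longer episodes lead to a hold and a dose decrement. The trigger in these rows is the count.

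Protocol 9.1 sets the reporting rule: "Laboratory findings should not be recorded as AEs unless corrective action is required", or the treating physician judges the event clinically significant. The examples of corrective action are transfusion, starting antibiotics or another treatment, and hydration. A dose hold is not among them. A brief fall in count that leads to a hold, recovers untreated and is not judged clinically significant can therefore be handled correctly under both rules and leave no AE record. That hold has no place in the SAP's table.

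**3. Is the number of affected cycles available?** SAP 7.4.1 plans no such count, and an AE action field does not directly give one. The other items cannot replace it:

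- A cycle counts as dosed after one full daily dose. That is 1 of 5 planned oprozomib doses (1/5 = 20%) on 5/14, or 1 of 4 (1/4 = 25%) on 2/7. A cycle with every later dose held still counts.
- Total doses fall when doses are held, but also when treatment ends early. With assumed values on 5/14, 10 complete cycles give 10 × 5 = 50 doses, and 12 cycles with 10 doses held give 12 × 5 − 10 = 50. Duration of treatment would differ between these subjects, but neither summary gives the percentage of subjects or the number of cycles with a hold.

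**4. How are cycles counted when dexamethasone stops first?** Protocol 6.4.2 provides for permanent discontinuation of dexamethasone. It requires dexamethasone to stop when oprozomib is permanently stopped, but does not state the reverse, so oprozomib-only cycles can occur. Illustration with assumed values: 12 oprozomib cycles, dexamethasone stopped after cycle k. Share of oprozomib cycles not counted if both drugs are required = 1 − k/12.

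| k | Counted, both drugs required | Counted, oprozomib separately | Share not counted if both required |
|---|---|---|---|
| 2 | 2 | 12 | 83% |
| 4 | 4 | 12 | 67% |
| 8 | 8 | 12 | 33% |

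The loss arises only if the phrase is read as requiring both drugs.

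**The case against.** The case on the other side is substantial, and much of it stands.

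- *A reader might infer that held doses vanish from the record of treatment.* They do not. Duration and total doses are not AE-based, held doses lower the total, and SAP 7.1 puts all eCRF data into subject listings. What is missing is the summary of holds and reductions.
- *A reader might take it as settled that the SAP counts cycles by both drugs together.* The wording does not settle this. The opening sentence of 7.4.1, and the duration and total-dose items, use the same pairing of drugs where a per-drug meaning is natural. This is an ambiguity to close.
- *A reader might assume that all count-triggered holds are missed.* Many may be captured. The examples in 9.1 are not exhaustive, and an ANC below 500 cells/mcL is Grade 4 neutropenia, which many investigators would call clinically significant. SAP 7.6.2 also summarises Grade 3 or higher laboratory toxicities directly. That table shows the low count, however, and not the hold.
- *A reader might extend the point to missed doses, delays for holidays or subject requests, and received-versus-planned dose.* Protocol 10.3.3 names only holds and reductions. The others would be additions to the protocol's plan and are not part of this departure.
- *A reader might infer an effect on the MTD or the response rate.* There is none. The MTD rests on DLTs in a window where delays are not permitted and subjects without a DLT who lack planned doses are replaced. The Cohort Safety Review Committee considers all available clinical data. ORR is estimated on the Safety Population by dose group, whatever this table shows.

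The objection does not supply the promised measure. Listings are not calculated percentages or cycle counts, and the SAP's own undertaking to document departures was not met.

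**Conclusion.** The point holds as a reporting departure. SAP 7.4.1 replaces an unrestricted protocol summary with an AE-linked one, omits the count of affected cycles, and does not say so. Followed as written, the AE-based table can under-count holds and reductions.

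The size of the under-count depends on the share of holds and reductions without an AE record. The documents give no such share, so no figure is offered; it could be small if sites record most of these low counts as adverse events. The direction rests on one assumption, that AE action fields are correctly completed where an AE exists. The percentages for uncounted cycles in the working are illustrations of one reading of ambiguous wording.

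No hypothesis, decision rule, MTD determination or ORR estimate is affected. The correction is still worth making, because the table supports a primary objective and the remedy is specific and cheap.

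**What to change.** In SAP 7.4.1:

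1. Derive dose holds and reductions separately for oprozomib and dexamethasone from the dosing records that already support the total-dose summary. Report the percentage of subjects and the number of cycles affected, by schedule and dose group, as Protocol 10.3.3 plans. Keep the AE action taken as the reason where one exists.
2. State that treatment cycles, and subjects dosed by cycle, are counted separately for oprozomib and for dexamethasone.
3. If the AE-based summary is kept instead, record it in the SAP as a change from Protocol 10.3.3, with the reason.

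The cost is SAP wording and one or two revised exposure tables. This assumes that the dosing records hold enough detail to identify holds and reductions. The total-dose item implies that such records exist, but the eCRF is not among the documents. Reported delivery may look slightly less favourable. No dosing rule changes.
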